4.0 Rockefeller University Conflict of Interest

4.1 Investigator Financial Conflict of Interest All KSP must complete an annual certification of their Significant Financial Interest ("SFI") disclosures in the University's online Research Administration System at <https://RAS.rockefeller.edu>. Disclosures also must be updated in connection with new human subjects research protocols ("Research Certification"), and within 30 days of discovering or acquiring a new SFI. To avoid delays in the IRB review process, when prompted by an email from [contact] requesting an updated Research Certification, KSP should click on the Research Certification link contained in that email notification, or go to <https://RAS.rockefeller.edu>, to (a) review and update his or her SFI disclosures or certify that he/she has no updates, as appropriate, and (b) indicate whether any of his/her SFI disclosures are reasonably related to the design, conduct, or reporting of the research protocol. If a KSP discloses a SFI that might constitute a conflict of interest with respect to the proposed protocol, he or she must e-mail a copy of the Lay Summary of the draft protocol to [name] ([contact]). Doing so will facilitate addressing COI issues in step with the development of the study protocol. Non-compliance or tardiness in making or updating COI disclosures will result in a delay in IRB review. **Institutional Conflict of Interest:**

As early as possible the PI (or a designee) preparing a clinical research protocol must review a list of entities in which The Rockefeller University has an Institutional Financial Interest at <https://icoi.rockefeller.edu/account/login.php>. If the proposed study involves any entity on that list, the PI (or designee) must notify [name], staff to the FCOI Committee, by e-mail [contact] and [name], Chair of the IRB, by email: [contact], provide the name(s) of the entities and a copy of the Lay Summary. Doing so will facilitate addressing institutional COI issues in step with the development of the study protocol. Failure to take steps to review and address potential institutional conflicts of interest will delay the IRB review process.

7.0 Study Description

7.1

Study Classification

Full Review

7.2

* Submission Request Category

Note: For each submission, please designate the level of review, or "Submission Request Category" you are requesting. When completing this field, please indicate the level of review you are requesting for the specific submission you are working on.

For example, if you are submitting an Expedited Amendment request to change the Key Study Personnel on your existing Full Board study, you should select "Expedited Review" in both the Amendment Submission Form and Study Application. The IRB will confirm an Expedited review of the Amendment submission is appropriate, and the overall study will remain classified as a full Board review. Please see the help bubble for guidance.

- Exempt from Review
- Exempt with Limited Review
- Expedited Review
- Not Human Subjects
- Full Review

7.3 * Lay Summary

Please provide a summary of your study in lay language. The summary should be no more than a half page (500 words or less) and should contain a clear statement of the rationale for the study.

Psoriasis is an immune-mediated disease of the skin that, even in mild disease, increases the risk of co-morbidities such as cardiovascular disease and metabolic derangements. Mild psoriasis tends to be treated with topical drugs, while moderate-to-severe disease is optimally treated with systemic immune modulators. However, the treatment of "mild" psoriasis needs to be re-thought because recent studies have revealed that mild psoriasis is characterized by stronger expression of pathogenic molecules, such as interleukin (IL)-17A, and higher numbers of T cells in the skin, compared to severe psoriasis. A key distinction between mild and severe psoriasis is now discovered to be the higher expression of negative immune regulatory genes in mild lesions. Therefore, targeted immune therapy with anti-IL-17A, which is highly effective in severe psoriasis, might be equally (or even more) effective in mild disease. Also, restoration of immune tolerance might be more easily achieved in mild disease. Thus, short-term anti-IL-17A treatment of mild psoriasis might prevent the recurrence and eventually cure the disease. The

aim of study is to test this hypothesis by exploring whether 3 months or 6 months of anti-IL17A treatment will prevent relapses after medication has been discontinued in mild psoriasis patients

7.4

* Public Health Impact Statement

Provide a brief plain language statement (100 words or less) of the value of the research proposed and its potential impact on population health. Additional instructions located in Help.

Mild psoriasis not only progresses to moderate-to-severe psoriasis but also precedes systemic inflammation that leads to psoriatic arthritis and cardiovascular comorbidities. By curing mild psoriasis with a short-term anti-IL-17A treatment, we may reduce the costs of treating psoriasis and associated medical conditions, including psoriatic arthritis, cardiovascular disease, and diabetes.

8.0

Screening for Expedited Review

Studies that may be reviewed by expedited review fall into 7 categories described in detail in 46CFR 8392. These include drawing of blood within prescribed limits, collection of samples such as saliva, mucosal and skin cells by scraping, and excreta or sweat. Data may be collected by physical sensors such as weighing, EKG, EEG, MRI, moderate exercise and strength testing, and body composition assessment. Collection of data from voice, video or image recordings obtained in research. Research on perception, cognition, social behavior employing surveys, interviews, focus groups and oral history.

Research may be conducted on data, documents, records or specimens that have or will be collected solely for non-research purposes in the course of medical treatment or diagnosis.

Note: Protocol studies that involve a drug that requires an IND, or that involve greater than minimal risk to participants, or that involve the use of X-rays or microwaves are not eligible for an expedited review.

* Based on the above information, does your research study qualify for an "expedited" review?

- Yes
- No
- Not Sure

9.0

Clinical Trial Registration

9.1

Clinical Trial Registration

The types of studies listed below must be registered at www.ClinicalTrials.gov

- Study involves testing of FDA regulated drugs or biologics (See HELP)

- Study is funded by the NIH, and meets the definition of a "clinical trial" (see HELP)
- Study meets the ICMJE definition of a "clinical trial" (See HELP)
- None of the above

If you selected 1, 2, or 3, you must register your trial with [ClinicalTrials.gov](https://clinicaltrials.gov) through the Rockefeller University institutional account. Please contact the Clinical Research Support Office [name] for assistance.

10.0

Study Overview/Summary

10.1 * Who initiated this study?

Please specify one:

- Principal Investigator Initiated
- Industry Initiated
- Other

10.2 * This study in collaboration with:

- Weill Cornell Medical College
- Memorial Sloan-Kettering Cancer Center
- Both Weill Cornell Medical College and Memorial Sloan-Kettering Cancer Center
- Neither Weill Cornell Medical College nor Memorial Sloan-Kettering Cancer Center

Please note: If any of the first three options is checked, you will be prompted to attach the **IRB of Record** forms later on in the submission. Links to these forms can be found in the Help link to the right.

10.3 * Are other institutions involved in the study?

- 1. No
- 2. Yes, and a federal, industry or private organization is administratively coordinating the study.
- 3. Yes, however, a federal, industry or private organization is not administratively coordinating the study.

10.4 * Is this a multi-center trial?

- Yes
- No

10.5 * Who (What) is to be studied?

- Human Subjects - including coded samples and/or data with links to Identifiers
- Deidentified Samples - unable to be linked to identifiers by receiver
- Data Only - unable to be linked to identifiers
- Identifiable samples or data for exemptions (per 104 (s)(4))

10.6 * Study Type:

- Interventional
 Observational

10.7 The initial date of IRB approval/determination was:

01/05/2017

10.8 * What is the expected duration of the study?

4 Years

10.9 * Are any of the following agents to be used in the study?

Check all that apply:

- Drug FDA Approved
 Approved Drug for Off-Label Purpose (This might require an IND)
 Investigational New Drug
 Biologic Agents
 Nutritional Supplements
 Placebo
 Vaccines
 No Agents

10.10 * Are investigational devices to be used in the study?

Yes No

10.16 Special Research Procedures

Does the study propose to directly involve participants in the following special research procedures?

- Recombinant DNA
 Gene Therapy
 Fetal Tissue
 Embryonic Stem Cells
 Induced Pluripotent Stem Cells
 CRISPR-Cas9

If any item is checked, please see Help for details.

10.17 * Radioactive Isotopes Involved

Will participants be exposed to any radiation other than routine x-rays solely for clinical care purposes?

Yes No

11.0 Interventional

11.1 *Interventional, please specify:

- Open Label
- Single Blind
- Double Blind
- Other

12.0 Objectives and Rationale

12.1 * Overview

Briefly state the *purpose of this study*. Give enough background and rationale to provide both scientists and lay members of the IRB and ACCTS with the basis for exposing human participants to the risks involved.

Psoriasis is an immune-mediated disease of the skin that, even in mild cutaneous form, increases the risk of co-morbidities such as cardiovascular disease and metabolic derangements that likely result from systemic inflammation. Treatments differ between “polar” forms of psoriasis, i.e., mild psoriasis tends to be treated with topical drugs, while moderate-to-severe psoriasis is optimally treated with systemic immune modulators. While it is recognized that topical agents are far less effective than most biologics that antagonize cytokines (anti-TNF, anti-IL-12/23, anti-IL-17), the decision not to treat “mild” patients (here mild psoriasis is defined by psoriasis affected Body Surface Area (BSA) less than 10% and Psoriasis Area and Severity Index (PASI) between 6 and 12) has been based on 1) significant toxicity associated with historical agents such as cyclosporine or methotrexate, so treatment was done only for patients for whom topical agents were not practical (>10% body surface) and 2) the perception that “mild” psoriasis involves less severe inflammation in the skin than in patients with more extensive psoriasis.

The treatment of “mild” psoriasis needs to be re-thought because 1) inflammation is not limited only to the skin as evidenced by the risk for co-morbid inflammatory conditions; 2) patients that develop psoriatic arthritis often come from the pool of “mild” patients, as the extent of psoriasis skin is often <10% in this group of patients that may be as much as 1/3 of all psoriatics; 3) current generation cytokine antagonists such as Ustekinumab and Secukinumab are not only highly effective in treating cutaneous psoriasis, but they are also extremely well tolerated drugs with minimal systemic toxicity profiles – this has changed the risk/benefit equation of treating mild patients with systemic drugs; 4) a new study we have conducted has directly compared IL-17-mediated inflammation and overall disease burden in skin lesions using global gene expression profiling of mild vs. moderate-to-severe lesions.

Surprisingly, mild psoriasis was characterized by significantly higher IL-17A expression, stronger expression of the core psoriasis transcriptome, and by higher numbers of T-cells in skin lesions. In contrast, severe psoriasis was characterized by stronger expression of some epidermal response genes (TGFA, CALM1, SMPD3 & IL1RL2). However, a key molecular distinction between mild and severe psoriasis was higher expression of negative immune regulatory genes (CTLA4, PD-L1 & CD69) in mild lesions compared to severe psoriasis lesions.

These data have relevant implications for therapy of psoriasis—first they suggest that anti-IL-17A approaches used in severe psoriasis might be equally (or even more) effective in mild psoriasis. Secondly, restoration of immune tolerance might be more easily achieved in mild psoriasis due to higher “regulatory” immune tone that effectively prevents unbounded T-cell expansion. Thus, short-term anti-IL-17A treatment of mild psoriasis might prevent the recurrence and eventually cure psoriasis. The aim of the study is to test this hypothesis by exploring whether 3 months or 6 months of Secukinumab treatment will prevent relapses after medication has been discontinued in mild psoriasis patients.

12.4 * Engaging Stakeholders: Describe any plans to engage other stakeholders (Scientists, practitioners, patients, advocacy groups, etc.) for hypothesis generation, or feasibility purposes.

We will engage stakeholders, including participants, their families, their health care providers, and the study sponsor, and to assure safe progression of the study and to address any concerns may arise.

12.5 * Hypothesis

Describe the *research hypothesis* in a single sentence.

COSENTYX (secukinumab) is efficacious in treating mild, chronic plaque type of psoriasis in adults.

12.6 * Aim(s)

Indicate how you will *address the hypothesis* (e.g., to compare groups, to estimate a parameter, to ascertain feasibility). Since the sample size determination is usually based on the primary aim only, the primary aim should be sufficient to justify the study.

- 1) To evaluate the efficacy of secukinumab for the complete resolution of mild plaque-type psoriasis after 3 months of secukinumab treatment by comparing the secukinumab-receiving mild psoriasis subjects (Group 1) and the placebo-receiving mild psoriasis subjects (Group 2).
*Mild psoriasis - psoriasis affected Body Surface Area (BSA) less than 10% and Psoriasis Area and Severity Index (PASI) between 6 and 12.
*Group 1 : 6 months secukinumab + 12 months observation
*Group 2 : 3 months placebo + 3 months secukinumab + 12 months observation
- 2) To explore whether secukinumab will prevent relapses after medication has been discontinued in subjects with mild plaque-type psoriasis.
- 3) To compare frequency of relapse between subjects who achieve a score of 0 (clear) on IGA (Investigator's Global Assessment) and subjects who do not achieve a score of 0 (clear) on IGA, within each group (Group 1 (6 months secukinumab) and Group 2 (3 months Placebo + 3 months secukinumab)).
- 4) To compare frequency of relapse between subjects who achieve a score of 0 (clear) on IGA between group 1 and group 2 (Group 1 (6 months secukinumab) and Group 2 (3 months Placebo + 3 months secukinumab)).
- 5) To evaluate the safety of secukinumab for the treatment of subjects with mild plaque-type psoriasis comparing the secukinumab-receiving mild psoriasis subjects (Group 1) and the placebo-receiving mild psoriasis subjects (Group 2) for 3 months.

12.7 * Primary Outcome(s)

Indicate which *variable(s)* will be assessed to judge the primary specific aim. Give measurement units, if applicable.

- 1) The proportion of subjects who have a reduction of 75% or more from baseline in the psoriasis area-and-severity index score (PASI 75) at week 12 (*primary endpoint*)¹
- 2) The proportion of subjects who have a reduction of 90% or more from baseline in the psoriasis area-and-severity index score (PASI 90) at week 12²
- 3) The proportion of subjects who achieve a score of 0 (clear) on a 5-point modified investigator's global assessment (IGA) at week 12³

1,2,3The 3 co-primary endpoints are subject to a step-down hierarchical closed testing procedure. (Primary objective is achieved if any null hypothesis is rejected following the order: PASI75, PASI90, IGA0).

12.8 * Secondary Outcome(s)

Indicate which *additional variable(s)* will be assessed to judge the secondary outcome(s). Give measurement units, if applicable.

- 1) The proportion of subjects who experience a psoriasis relapse at any time between week 24 and week 72. Psoriasis relapse is defined as loss of > 50% of the initial PASI improvement measured at week 24.
- 2) Severity of the relapses over the observation period.
- 3) Extent of relapse over the observation period.
- 4) Elapsed time from week 24 until relapse occurs before week 72, measured in weeks.
- 5) The proportion of subjects who achieve a PASI 100 or PASI 90 response at week 12
- 6) Frequency and severity of all AEs and SAEs that occur during the whole trial including the observational period (AEs and SAEs include but not limited to comorbidities, such as hypertension, diabetes, and cardiovascular diseases).

12.9 * Methods and Procedures

Please provide a description of the laboratory and clinical analyses and procedures that will be performed. Include the role of external collaborators and consultants when appropriate. Please refer to Help text for Guidance.

The trial will be conducted as a unicenter, randomized, double-blind, parallel-group, placebo-controlled exploratory study of Secukinumab in subjects with mild plaque-type psoriasis. The purpose of the study is to evaluate the efficacy and the safety of Secukinumab for 3 or 6 month treatment periods, and to explore whether relapse occurs after the medication has been discontinued, during the subsequent 12 month observation period.

Arms: (Group 1: 6 months of Secukinumab) vs. (Group 2: 3 months of Secukinumab). Patients will be randomly assigned in a 1:1 ratio to Group 1 or Group 2. Group 1 receives Secukinumab at a dose of 300 mg with injections administered once weekly at baseline and at weeks 1, 2, 3, and 4 and then every 4 weeks for 6 months of period until week 12.

Patients randomly assigned to Group 2 will receive placebo injections corresponding to the Group 1 regimen until week 8 in order to maintain a double-dummy design until week 12. However, Group 2 will receive Secukinumab at a dose of 300 mg with injections administered **once weekly at week 12 and at weeks 13, 14, 15, and 16 and then every 4 weeks for 3 months** of period. Both group 1 and 2 discontinue Secukinumab after week 24 being observed from week 25 to week 72 (48 weeks).

Both Group 1 and Group 2 patients will not receive topicals or any other therapies except Secukinumab during the study periods, including placebo and observation periods.

Secukinumab is dosed weekly for the first 4 weeks (ramp up) the monthly (maintenance). In order to maintain the blind for the 2 dose groups, group 1 will resume weekly injection weeks 12 through 16. The injections given at weeks 13, 14, and 15 will be placebo.

Visit	Group 1		Group 2		Skin biopsy & blood
1	Screening	Screening			
2	baseline	baseline	Secukinumab 300 mg	Placebo	Skin biopsy & blood

3		week 1	Secukinumab 300 mg	Placebo	
4		week 2	Secukinumab 300 mg	Placebo	
5		week 3	Secukinumab 300 mg	Placebo	
6	month 1	week 4	Secukinumab 300 mg	Placebo	
7	month 2	week 8	Secukinumab 300 mg	Placebo	
8	month 3	week 12	check primary endpoint (IGA 0,1 at week 12)		Skin biopsy & blood
			Secukinumab 300 mg	Secukinumab 300 mg	
9		week 13	Placebo	Secukinumab 300 mg	
10		week 14	Placebo	Secukinumab 300 mg	
11		week 15	Placebo	Secukinumab 300 mg	
12	month 4	week 16	Secukinumab 300 mg	Secukinumab 300 mg	
13	month 5	week 20	Secukinumab 300 mg	Secukinumab 300 mg	
14	month 6	week 24	Secukinumab 300 mg	Secukinumab 300 mg	Skin biopsy & blood
15	month 9	week 36			
16	month 12	week 48	observation	observation	
17	month 15	week 60			
18	month 18	week 72	check secondary endpoint (recurrence)		Skin biopsy & blood
	*Optional skin biopsy and blood : when recurrence occurs after week 24				

Study Visits

Visit 1--Screening Visit/Enrollment

- Vital signs (weight, height, blood pressure, temperature, heart rate, respiration)
- Physical exam and questions your general health
- Serum pregnancy if female of child-bearing potential
- POCT HIV
- Blood for Hepatitis B (antibody as well antigen) and C, Comprehensive metabolic panel, Lipid panel, Hgb A1c, CBC and optional QuantFERON-TB Gold (only if no PPD screen)
- Assessment of psoriasis status using several scales: Investigator Global Assessment (IGA), Psoriasis Area and Severity Index (PASI) with BSA, Dermatology Life Quality Index (DLQI), PASE
- PPD / TB skin test or QuantIFERON-TB Gold

Visit 1.1--PPD Reading Visit

- If PPD was placed at Screening Visit, PPD reading 48 hours later
- Chest X-Ray. (If PPD Positive)

Visit 2--Baseline visit (and first dose)

- Medications history
- Physical exam (symptom driven as indicated)
- Vital signs (weight, body temperature, heart rate and blood pressure)
- POCT Pregnancy
- Fasting Blood PAX DNA/RNA, CBC, SST (serum storage) sample, Comprehensive Metabolic Panel, Lipid panel, and Hgb A1c.
- Two 6mm skin biopsies, 1 lesional, 1 non-lesional.
- Medical photography
- Assessment of psoriasis, PGA, PASI with BSA, PASE, DLQI
- Adverse event assessment
- Dose of Secukinumab or placebo by subcutaneous injection.
- Observation period of 15 minutes (+/- 5 minutes) post study drug administration
- Subject will be offered a meal at end of visit.

Visit 3 to 7 and 9 to 13 --(Week 1 to 8 and 13 to 20)

- Physical exam (symptom driven as indicated)
- Vital signs (blood pressure, temperature and pulse).
- POCT Pregnancy
- Assessment of psoriasis, PGA, PASI with BSA, PASE, DLQI
- Adverse event assessment
- Dose of Secukinumab 300 mg or placebo by subcutaneous injections

Visit 8 and 14 --(Week 12 and 24)

- Physical exam (symptom driven as indicated)
- Vital signs (blood pressure, temperature and pulse).
- POCT Pregnancy
- Fasting Blood: Comprehensive metabolic profile, CBC, lipids and HgB A1c.
- Research blood
- Two 6mm skin biopsies, 1 lesional, 1 non-lesional. The lesional sample will be taken from the area the lesions were before.
- Medical photography
- Assessment of psoriasis, PGA, PASI with BSA, PASE, DLQI
- Adverse event assessment
- Dose of Secukinumab 300 mg or placebo by subcutaneous injection
- Observation period of 15 minutes (+/- 5 minutes) post study drug administration week 12 only
- Subject will be offered a meal at end of visit

Visit 15,16, and 17 —(Week 36, 48 and 60) Observation

- Physical exam (symptom driven as indicated)
- Vital signs (blood pressure, temperature and pulse)
- POCT Pregnancy
- Assessment of psoriasis, PGA, PASI, with BSA, PASE, DLQI
- Adverse event assessment

Visit 18 --(Week 72)

- Physical exam (symptom driven as indicated)
- Vital signs (blood pressure, temperature and pulse)
- POCT Pregnancy

- Fasting Blood: Comprehensive metabolic profile, CBC, lipids and Hgb A1c
- Research Blood
- Skin biopsy is optional when recurrence occurs after Week 24. Two 6mm skin biopsies, 1 lesional, 1 non-lesional. The lesional sample will be taken from the area the lesions were before.
- Medical photography
- Assessment of psoriasis, PGA, PASI with BSA, PASE, DLQI
- Adverse event assessment
- Observation period
- Subject will be offered a meal at end of visit.

*Visit window will be +/- 1 day for weekly visits (weeks 1, 2, 3, 4, 13, 14, 15,16) and +/- 2 days for all other visits (weeks 8, 12, 20, 24, 36, 48, 60, 72).

Unscheduled Visit--(as necessary)

Subjects will return to RUH for evaluation and/or additional blood work, as per the PI's discretion.

Relapse Visit

- Research Blood
- Skin biopsy is optional. Two 6mm skin biopsies, 1 lesional, 1 non-lesional.
- Medical photography
- Assessment of psoriasis, PGA, PASI with BSA, PASE, DLQI
- Adverse event assessment

Early Termination visit

- Research Blood
- Skin biopsy is optional. Two 6mm skin biopsies, 1 lesional, 1 non-lesional.
- Medical photography
- Assessment of psoriasis, PGA, PASI with BSA, PASE, DLQI
- Adverse event assessment

Translational research: 6-mm punch skin biopsies from lesional and non-lesional skin and blood samples will be obtained at baseline and weeks 12, 24, 72, at the time of psoriasis relapses, and at early termination. Genomic profiling of psoriasis skin will be conducted with the Affymetrix Human Genome U133 Plus 2.0 Array and RT-PCR. The phenotypes of activated T cells and regulatory T cells in psoriasis patients' blood will be studied by flow cytometry. Inflammatory and cardiovascular proteins in the blood will be investigated to develop a biomarker with Proximity Extension Assay technology (OLINK®).

Structure: Double Blind, Two-arm parallel group design, Randomized 1:1.

12.10 * Data Analysis

Describe method(s) of data analysis.

For the comparison between proportions a Fisher exact test will be performed in any case. The results will be presented as contingency tables and odd ratios will be calculated. 95% Confidence Intervals will be provided. To achieve the primary objective

The comparison between times of relapse must be done using a Wilcoxon-Mann-Whitney test. A Kaplan Meier analysis will be used to establish the relapse survival curve for each group and

the log-rank test will be made. A step-down hierarchical closed testing procedure will be done considering the order: PASI75, PASI90, IGA0.

12.11 * Explain the rationale for the choice of statistical measures and the number of participants proposed for the study, including the power calculations when applicable.

1. Sample Size Calculation for Primary Objective/First outcome (3 co-primary endpoints are subject to a step-down hierarchical closed testing procedure)

Langley et al. (2014) presented the results of two Phase 3 trials for Secukinumab: ERASURE and FIXTURE. Among others outcomes Langley reported the proportion of subjects with moderate or severe Psoriasis who achieve PASI75 (PASI score improvement over 75%) after 12 weeks of treatment in the 2 cohorts treated with Secukinumab 300 mg and the 2 Placebo cohorts with 245, 323, 246 and 324 subjects respectively. The worst scenario observed on Langley's results is: largest Placebo proportion=0.05 and smallest Secukinumab proportion=0.77. Assuming Langley's results as preliminary data, to find significant differences between groups by using a one-tail Fisher exact test with power equal to 0.95 and 99.9% of significance level, a sample size of 19 patients at each group (N=38) will be required. Considering the 5.6 % of dropout reported by Langley will be necessary to recruit 20 patients for each group (N=40). Power analysis for 3 co-primary endpoints and 19:19 patients is reported in the following table:

ENDPOINT	TREATMENT OBSERVED PROPORTION *	PLACEBO OBSERVED PROPORTION *	OBSERVED EFFECT SIZE*	SIGNIFICANCE LEVEL	POWER	DETECTABLE EFFECT SIZE
PASI 75	0.77	0.05	0.72	0.05	0.8	0.49
				0.05	0.9	0.55
				0.05	0.95	0.60
				0.01	0.8	0.42
				0.01	0.9	0.48
PASI 90	0.54	0.02	0.52	0.05	0.8	0.4
				0.05	0.9	0.47
				0.05	0.95	0.52
				0.01	0.8	0.52
				0.01	0.9	0.59
IGA0	0.24	0.01	0.23	0.05	0.8	0.37
				0.05	0.9	0.44
				0.05	0.95	0.50
				0.01	0.8	0.50
				0.01	0.9	0.56
				0.01	0.95	0.61

OR

ENDPOINT	TREATMENT OBSERVED PROPORTION *	PLACEBO OBSERVED PROPORTION *	OBSERVED EFFECT SIZE*	SIGNIFICANCE LEVEL	ESTIMATED POWER TO DETECT OBSERVED EFFECT SIZE
PASI 75	0.77	0.05	0.72	0.05	0.99
				0.01	0.99

PASI 90	0.54	0.02	0.52	0.05	0.99
				0.01	0.94
IGA 0	0.24	0.1	0.14	0.05	0.46
				0.01	0.25

* Langley et al. (2014)

2. Power Analysis for Exploratory Objectives/First outcome

Assuming the proportion of 300 mg secukinumab patients who achieve PASI 100 at week 24 as reported by Langley (0.4), the allocation ratio of subjects who achieve PASI 100 and subjects who not achieve PASI 100 for Group 1 (6 month of Secukinumab) will be 8:11. On that case a Fisher exact test to compare the proportion of patients who experience relapse with power equal to 0.80 and 95% of significance level will be able to detect significant differences only if the following relationship between proportions is observed:

Proportion of patients from Group 1, who achieve PASI 100 at week 24 and experience relapse	Proportion of patients from Group 1, who not achieve PASI 100 at week 24 and experience relapse
0.00	0.45
0.13	0.73
0.25	0.82
0.38	0.91
0.50	1.00

Assuming the proportion of 300 mg secukinumab patients who achieve PASI 100 at week 12 as reported by Langley (0.3), the allocation ratio of subjects who achieve PASI 100 and subjects who not achieve PASI 100 for Group 1 (6 month of Secukinumab) will be 6:13. On that case a Fisher exact test to compare the proportion of patients who experience relapse with power equal to 0.80 and 95% of significance level will be able to detect significant differences only if the following relationship between proportions is observed:

Proportion of patients from Group 2, who achieve PASI 100 at week 24 and experience relapse	Proportion of patients from Group 2, who not achieve PASI 100 at week 24 and experience relapse
0.00	0.54
0.17	0.77
0.33	0.85
0.50	1.00

With the previous assumptions, the allocation ratio of subjects who achieve PASI 100 in Groups 1 and 2 will be 8:6. On that case a Fisher exact test to compare the proportion of patients who experience relapse with power equal to 0.80 and 95% of significance level will be able to detect significant differences only if the following relationship between proportions is observed:

Proportion of patients from Group 1 who achieve PASI 100 at week 24 and experience relapse	Proportion of patients from Group 2 who achieve PASI 100 at week 24 and experience relapse
0.00	0.67
0.13	0.83
0.25	1.00

3. Power Analysis for Exploratory Objective/Second outcome

To compare the time to relapse between groups with a sample size of 19:19 a Wilcoxon-Mann-Whitney test for nonrelated samples with power equal to 0.8 and 95% of significance level will be able to detect differences only if the effect size observed is equal or larger than 0.96

12.12 * Will samples be coded?

Yes No

If Yes, Please describe coding scheme consistent with GCP. If samples will not be coded, please provide justification for this proposed departure from GCP practice.

Samples will be coded using GCP with the following sequence

NSK__-001. NSK__-002, etc.

If available, upload the Data and Sample Sharing Management Plan approved by RU IT.

Version	Title	Category	Expiration Date	Document Outcome	Checked Out	View Document
No Document(s) have been attached to this form.						

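### Aim 3 tests clearance against relapse only in two separate tests of about 19 patients; the stated 0.80 power does not reproduce, and an added test stratified by group would be stronger

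*Combined protocol and SAP*

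**What the plan says.** Section 12.6, Aim 3, compares relapse frequency between subjects who reach IGA 0 and "subjects who do not achieve a score of 0 (clear) on IGA, within each group". Section 12.10 gives the method: "For the comparison between proportions a Fisher exact test will be performed in any case". It names no stratified or pooled test of clearance against relapse. Its Wilcoxon and log-rank analyses are described for times to relapse by treatment group, not for clear against not-clear patients.

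Section 12.11, item 2, gives the power for this aim. It switches the classifier from IGA 0 to PASI 100. It expects the ratio of "subjects who achieve PASI 100 and subjects who not achieve PASI 100 for Group 1 (6 month of Secukinumab) will be 8:11", and a second split that the text gives as "for Group 1 (6 month of Secukinumab) will be 6:13" although the table beneath is headed Group 2. For each split it lists pairs of relapse proportions and states power 0.80 at what it calls a 95% significance level. Whether the test is one- or two-sided is not stated.

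Both splits add to 19, the figure from the primary calculation: "a sample size of 19 patients at each group (N=38) will be required".

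**The concern.** Both groups stop secukinumab at week 24, are followed to week 72 and share one relapse definition. Whether clearance predicts less relapse can therefore be asked once across all 38 patients, with randomised group as a stratum, as well as within each group. As planned, each test sees half the patients, and no rule says how two differing p-values would be combined.

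Two things are at stake. The plan credits each within-group test with power that it does not have at the tabulated differences. And under one and the same true link in both groups, a common outcome is one significant and one non-significant test, which could be misread as a difference between 3 and 6 months of treatment.

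**Working it through.** **Inputs.** Splits 8:11 and 6:13 (12.11; the second read as Group 2, following its table headings). They follow from 19 × 0.4 = 7.6 and 19 × 0.3 = 5.7. The 19 per group is 20 × (1 − 0.056) = 18.9. Alpha is 0.05, two-sided unless said otherwise. Relapse pairs are those of 12.11. Any other relapse rate below is an assumption, since the plan gives none.

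**Method.** Separate tests: power = Σ Bin(a; n₁, p₁) · Bin(b; n₂, p₂) over all tables with Fisher p ≤ 0.05. Stratified test: condition on the total relapses in each group, convolve the two hypergeometric distributions of relapses among clear patients, take the two-sided exact p-value, and sum over all four binomials.

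**1. The plan's 0.80.** Exact two-sided power is 0.60, 0.67, 0.64, 0.63 and 0.64 for the five 8:11 pairs, and 0.62, 0.67, 0.58 and 0.66 for the four 6:13 pairs. One-sided tests give 0.60–0.75 and 0.60–0.74, so sidedness does not explain the gap.

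The 0.50 v 1.00 rows can be checked by hand. With 8:11, all 11 not-clear patients relapse, and the test is significant when at most 4 of 8 clear patients do: (1 + 8 + 28 + 56 + 70)/256 = 163/256 = 0.637. With 6:13 it is at most 3 of 6: 42/64 = 0.656.

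**2. Where the pairs come from.** Each is the smallest observed difference with p ≤ 0.05.
- 0/8 v 5/11: p = (462 + 56)/11,628 = 0.044. With 4/11, p = (330 + 70)/3,876 = 0.10.
- 1/6 v 10/13: p = (1,716 + 78 + 1,287)/75,582 = 0.041. With 9/13, p = 0.057.

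True rates placed on the boundary of significance give power of about 0.6, not 0.80.

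**3. Stratified test at the plan's pairs** (at least one = 1 − (1 − a)(1 − b)):

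| 8:11 pair | 6:13 pair | Separate | At least one, uncorrected | Stratified |
|---|---|---|---|---|
| 0.00/0.45 | 0.00/0.54 | 0.60, 0.62 | 0.85 | 0.98 |
| 0.13/0.73 | 0.17/0.77 | 0.67, 0.67 | 0.89 | 0.965 |
| 0.25/0.82 | 0.33/0.85 | 0.64, 0.58 | 0.85 | 0.92 |
| 0.50/1.00 | 0.50/1.00 | 0.64, 0.66 | 0.88 | 0.98 |

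The remaining 8:11 row, 0.38/0.91, has no exact partner; set beside 0.33/0.85 it gives 0.91.

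**4. Assumed relapse rates, the same in both groups:**

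| Clear v not clear | Separate | At least one | At least one, Bonferroni | Both | Stratified |
|---|---|---|---|---|---|
| 0.25 v 0.75 | 0.48, 0.48 | 0.73 | 0.62 | 0.23 | 0.85 |
| 0.25 v 0.70 | 0.37, 0.38 | 0.61 | 0.51 | 0.14 | 0.75 |
| 0.40 v 0.85 | 0.44, 0.46 | 0.70 | 0.57 | 0.20 | 0.78 |

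Exactly one significant test is at least one minus both: 0.73 − 0.23 = 0.50, 0.61 − 0.14 = 0.47 and 0.70 − 0.20 = 0.50. At 0.50 v 0.80 the stratified test has only 0.41.

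**5. Error rate and sensitivity.**
- With equal relapse rates of 0.3 to 0.8, the stratified exact test rejects with probability 0.027–0.038, so the gain is not bought with false positives.
- The only IGA 0 rate in the plan is 0.24 at week 12: 19 × 0.24 = 4.6, about 5:14, assumed for both groups. At 0.25 v 0.75 this gives 0.46 per test and 0.77 stratified.
- With assumed further losses to 7:9 and 5:11, the same rates give 0.42 and 0.40 against 0.73.
- If 0.25 v 0.75 holds in Group 1 only, and relapse in Group 2 is 0.50 whether clear or not (assumed), the stratified test has about 0.30 against 0.48 for the Group 1 test.

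**The case against.** The strongest reply is that within-group comparison is the stated aim. Exposure differs (6 v 3 months of secukinumab), the study asks whether 3 or 6 months prevents relapse, and Aim 4 compares clear patients between the groups. Clearance may mean something different after each duration, and a common odds ratio answers a different question. This stands: it is a reason to add a stratified test, not to replace or demote the within-group ones.

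Second, a reader might infer that the trial will most likely find no link even if a large one exists. The figures do not support that. At least one separate test is significant with probability 0.61–0.73 at the three assumed scenarios, and 0.85–0.89 at the plan's matched pairs. Low power describes one named test. The fairer comparator is the two tests read together with Bonferroni control, 0.51–0.62 against 0.75–0.85. The gain is real but smaller than a one-test comparison suggests.

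Third, the aim is exploratory, the trial is sized on week-12 PASI 75, and 12.11 openly says that only large differences are detectable. That lowers the urgency. It does not rescue the 0.80, which is wrong for the tables it labels.

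**Conclusion.** The point holds as an omission and a misstated power. Aim 3 has no combined test. Its within-group tests have 0.58–0.67 at the plan's own pairs rather than 0.80, and one test stratified by group has 0.92–0.98 at the matched pairs.

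A reader might summarise the gain as power rising from about 0.45 to 0.80. Neither figure is in the documents. They correspond to an assumed gap of about 50 points in relapse (for example 0.30 v 0.775) and should not be quoted without it. At smaller gaps, such as 0.50 v 0.80, stratifying does not rescue the aim.

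The figures assume a similar link in both groups, PASI 100 splits standing in for IGA 0, and 38 evaluable patients. The last rests on a dropout rate applied to the week-12 sample size, whereas relapse is followed to week 72. The sensitivity cases lower both sets of powers but leave the advantage in place.

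**What to change.** In Aim 3 and 12.10, add as the overall test of clearance against relapse an exact conditional (Mantel-Haenszel type) test stratified by randomised group, with a common odds ratio and confidence interval. Add a log-rank test stratified by group for time to relapse, clear against not clear. Keep the two within-group comparisons as planned, and report the difference between the two odds ratios as a heterogeneity check.

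In 12.11, restate the 0.80: either give the exact powers of 0.58–0.67, or label the pairs as the smallest observed significant differences. State the sidedness, correct the group label on the 6:13 split, and say whether IGA 0 or PASI 100 defines clear and at which week.

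The cost is wording and one extra analysis, with no new patients, visits or data. Section 17.1 says recruitment is closed, so the analysis is the practical place to gain power. The change should be fixed before relapse results are examined by group or clearance. The downside is the loss of power if the link is confined to one group, which is why the within-group results stay in the report.
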